5.3.2. Preparation and Dispensing

Study medication will first be dispensed at the baseline visit (Day 1) after all baseline assessments have been completed. Treatment assignments will be made in accordance with the randomization sequence. Every blister card supplied to the site will have a unique number. The site will select a weight-based dosing regimen within the IVR/IWR system, and the IVR/IWR system will assign a container number that contains the indicated regimen. The weight-based dosing regimen selected at the start of the trial will continue to be applied throughout the trial; weight fluctuations of the subjects will not be considered to reassign a subject to a different weight based dosing group (ie, ≥45 kg body weight or <45 kg body weight).

At each subsequent medication dispensing visit (Day 8/Visit 3, Day 15/Visit 4, and Day 22/Visit 5), subjects will be assigned one blister card for the following study week. The IVR/IWR system will cap the total daily dosage allowed so subjects cannot be prescribed a dose higher than the maximum dose allowed per protocol (ie, subjects <45 kg cannot exceed 80 mg total daily dose and subjects ≥45 kg cannot exceed 160 mg total daily dose). The system will also not allow fixed dosing cards to be dispensed when there is an incremental jump of more than 20 mg/day compared to the last fixed dosing card dispensed (ie, a 120 mg/day fixed dose card could not be dispensed if the last fixed dose card dispensed

was an 80 mg/day card). The only exception to this rule is for subjects ≥ 45 kg where an increase from 120 mg/day to 160 mg/day will be allowed on Day 14 of the study. In addition, the IVR/IWR system will not allow more than one blister card at a time to be issued to a subject.

On Day 1 (Baseline Visit), a single titration card will be dispensed based on the subject's weight (subject ≥ 45 kg or < 45 kg) for the first week of dosing (see Table 1 and Table 2 below). The titration cards that will be used for the first week of the trial will have a maximum of 80 mg/day for subjects ≥ 45 kg and a maximum of 60 mg/day for subjects < 45 kg.

Table 1. ≥ 45 kg Titration Regimen for Day 1/Visit 2

Day	AM Dose (mg)	PM Dose (mg)	Total Daily Dose (mg)
1	-	20	20
2	20	20	40
3	20	20	40
4	20	40	60
5	20	40	60
6	40	40	80
7	40	40	80
8	40	40	80
9	40	40	80
10	40	40	80

Table 2. < 45 kg Titration Regimen for Day 1/Visit 2

Day	AM Dose (mg)	PM Dose (mg)	Total Daily Dose (mg)
1	-	20	20
2	20	20	40
3	20	20	40
4	20	20	40
5	20	40	60

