9.6.1. Analysis of Primary Endpoint

The primary efficacy endpoint is change from baseline in the YMRS score. The primary time point is Week 4. All other collection time points will be considered secondary.

Analysis of change from baseline in the YMRS score will be conducted using Statistical Analysis System (SAS) PROC MIXED to fit a mixed model repeated measures analysis of covariance (ANCOVA) with treatment, visit and visit-by-treatment interaction, and weight category as fixed effects and baseline score as a covariate. Subject effect will enter the MMRM model as a random effect. The estimation method used will be restricted maximum likelihood. An unstructured covariance matrix will be used in the REPEATED statement. In case SAS PROC MIXED fails to converge, other covariance matrix structures will be considered in the sequence of Toeplitz, First-Order Autoregressive, and Variance Components. The EMPIRICAL option will be specified to compute the estimated variance-covariance matrix of the fixed-effects parameters. Type III sums of squares will be used to test both main effects and interactions. The primary comparison will be between ziprasidone and placebo at Week 4, conducted as a two-sided test at 5% level of significance. Based on the specified model, the point estimate and 95% confidence interval (CI) for the difference in means between the two treatments will be constructed using the least squares means and appropriate standard errors.

If the test result is significant and in favor of ziprasidone, then efficacy of flexibly-dosed oral ziprasidone in the treatment of children and adolescents with Bipolar I Disorder (current or most recent episode manic) will be established.

A sensitivity analysis will be done by adding an interaction term of treatment and weight category to the primary analysis model specified above. Supplemental analyses of the primary variable will be performed to support the robustness of the conclusions drawn from the primary mixed models repeated measures analysis described above. These supplemental analyses will include the following:

- Summaries of reasons for discontinuations by treatment group;
- Pattern-mixture ANCOVA analysis of change from baseline YMRS scores.

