8. STATISTICAL METHODOLOGY AND STATISTICAL ANALYSES

8.1. Statistical Methods

8.1.1. Mixed Model Repeated Measures Analyses (MMRM)

The endpoints including the primary, key-secondary, and secondary endpoints will be analyzed using a mixed model repeated measures analysis of covariance (MMRM); treatment, visit, visit-by-treatment interaction, and weight category as fixed effects and baseline score (with the exception of CGI-I score) as a covariate. Subject effect will enter the MMRM model as a random effect. The estimation method used will be restricted maximum likelihood. An unstructured covariance matrix will be used in the REPEATED statement. In case SAS PROC MIXED fails to converge, other covariance matrix structures will be considered in the sequence of Toeplitz, First-Order Autoregressive, and Variance Components. The EMPIRICAL option will be specified to compute the estimated variance-covariance matrix of the fixed-effects parameters. Type III sums of squares will be used to test both main effects and interactions.

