8.2. Statistical Analyses

8.2.1. Primary Analysis

The primary efficacy endpoint is change from baseline in the YMRS score. The primary time point is Week 4. The primary endpoint will be analyzed using the MMRM model described in [Section 8.1.1](#). The primary comparison will be between ziprasidone and placebo at Week 4, conducted as a two-sided test at 5% level of significance. Based on the specified model, the point estimate and 95% confidence interval (CI) for the difference in means between the two treatments will be constructed using the least squares means and appropriate standard errors.

If the test result is significant (p-value ≤ 0.05) and in favor of ziprasidone, then efficacy of flexibly-dosed oral ziprasidone in the treatment of children and adolescents with Bipolar I Disorder (current or most recent episode manic) will be established.

A sensitivity analysis will be done by adding an interaction term of treatment and weight category to the primary analysis model specified in [Section 8.1.1](#).

Supplemental analyses of the primary variable will be performed to support the robustness of the conclusions drawn from the primary mixed models repeated measures analysis described above. These supplemental analyses will include the following:

- Summaries of reasons for discontinuations by treatment group;
- Pattern-mixture ANCOVA analysis of change from baseline YMRS scores.

For the pattern-mixture analysis, grouping of the subjects on the basis of their dropout or missing-data patterns will be explored. ‘Patterns’ will be defined under the following two cases:

Case 1:

Pattern 1A - all subjects who have completed the study

Pattern 1B - all subjects who have discontinued the study

Case 2:

Pattern 2A - all subjects who have YMRS score for Week 3 or beyond.

Pattern 2B - all subjects who do not have data beyond Week 2.

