8.2.7. Summary of Efficacy Analyses

Table 2. Summary of Efficacy Analyses

Endpoint	Analysis Set	Statistical Method	Objective
Change from baseline in YMRS total score at Week 4	ITT	MMRM	Primary Analysis
Change from baseline in YMRS total score at Week 4	PP	MMRM	Supportive of Primary Analysis
Change from baseline in YMRS total score at Week 4 – Sensitivity analysis (without 18 subjects)	ITT	MMRM	Sensitivity analysis of primary endpoint
Change from baseline in YMRS total score at Week 4 with interaction term of treatment and weight	ITT	MMRM	Sensitivity analysis of primary endpoint
Change from baseline in YMRS total score at Week 4 – Pattern Mixture Analyses	ITT	MMRM	Supportive of Primary Analysis
Change from baseline in YMRS total score at Week 4 – Pattern Mixture Analyses	PP	MMRM	Supportive of Primary Analysis
Change from baseline to week 4 in the CGI-S score	ITT	MMRM	Key-Secondary Analysis
Change from baseline to week 4 in the CGI-S score	PP	MMRM	Supportive of Key-Secondary Analysis
Change from baseline in YMRS total score and CGI-S score at Weeks 1, 2 and 3	ITT	MMRM	Secondary Analysis
Change from baseline in YMRS total score and CGI-S score at Weeks 1, 2 and 3	PP	MMRM	Supportive of Secondary Analysis
CGI-I score at weeks 1, 2, 3 and 4	ITT	MMRM	Secondary Analysis
CGI-I score at weeks 1, 2, 3 and 4	PP	MMRM	Supportive of Secondary Analysis
CCI			

Descriptive summaries are not included in this summary.

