Appendix 1.1. Sample SAS Code for the MMRM Analyses

Sample SAS code to fit the mixed model repeated measures specified in [Section 8.1.1](#) is given below. The response variable chg is the change from baseline at the study visits, Trtpn is the treatment group, avisitn is the assigned visit and blwcat is baseline weight category.

For the variance-covariance matrix: test various structures, start with the UN=unstructured matrix, in the case SAS PROC MIXED fails to converge, other covariance matrix structures will be considered in the sequence of Toeplitz, First-Order Autoregressive, and Variance Components/Covariance structure.

```
PROC MIXED DATA=xxxx EMPIRICAL;
  class trtpn avisitn blwcat usubjid;
  model chg = trtpn avisitn wtcat trtpn*avisitn base/ ddfm=kr2;
  repeated avisitn /subject= usubjid r type=UN rcorr covb;
  lsmeans trtpn*avisitn trtpn/ pdiff CL;
RUN;
ODS OUTPUT Diffs=diff
      LSMEANS = lsmeans;
Run;
```

CCI

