Appendix 1.3. Sample SAS Code for the CGI-I Raw Scores MMRM Analyses

Sample SAS code to fit the MMRM model specified in 8.1.1 is given below, except there is no baseline in model. The response variable actual is the actual score at each study visit, Trtpn is the treatment group, avisitn is the assigned visit and blwcat is baseline weight category.

```
PROC MIXED DATA=xxxx EMPIRICAL;
  class trtpn avisitn blwcat usubjid;
  model actual = trtpn avisitn wtcat trtpn*avisitn / ddfm=kr2;
    repeated avisitn /subject= usubjid r type=UN rcorr covb;
    lsmeans trtpn*avisitn trtpn/ pdiff CL;
  RUN;
  ODS OUTPUT Diffs=diff
    LSMEANS = lsmeans;
  Run;
```

Appendix 1.4. Sample SAS Code for the Pattern Mixture Models Case 1 and Case 2

Description of variables:

The response variable chg is the change from baseline at the study visits, Trtpn is the treatment group, avisitn is the assigned visit and blwcat is baseline weight category.

Case 1: **dropout** variable defined as binary (0= All subjects who have YMRS score for Week 4, 1 = All subjects who do not have data at Week 4)

avgbase as average baseline value of all patients

pcomp1 as proportion completers in Ziprasidone (Number of completers in Zip/Total number of patients in Zip)

pdisc1 as proportion dropouts in Ziprasidone (Number of dropouts in Zip/Total number of patients in Zip)

pcomp2 as proportion completers in placebo

pdisc2 as proportion dropouts in placebo

pct_compldif as **pcomp1 - pcomp2**

pct_discdif as **pdisc1 - pdisc2**

Notes to the model below:

(1) The different estimates statements are used to illustrate how the construction of the last estimate statement ZIPRASIDONE vs PLACEBO Averaged over Patterns is done. Same for the difference of ZIPRASIDONE Averaged over Patterns and PLACEBO Averaged over Patterns.

(2) Case 1: As the dropout subgroup has no records on the last visit week 4, there are no corresponding coefficients, and these are hence ignored in estimate specification (in particular three-way interaction coefficients).

```

PROC MIXED DATA=xxxx EMPIRICAL;
  class avisitn trtpn usubjid blwcat dropout;
  model chg=blwcat base avisitn trtpn avisitn*trtpn
    dropout dropout*avisitn dropout*trtpn avisitn*trtpn*dropout / solution covb;
  repeated avisitn /subject= usubjid r type=UN;

estimate "ZIPRASIDONE in Completers"
intercept 1 base avgbase avisitn 0 0 0 1 trtpn 1 0 dropout 1 0 avisitn*trtpn 0 0 0 0 0 1 0

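### The treatment-by-weight sensitivity model holds the interaction equal at Weeks 1 to 4, so a Week 4 weight-group result taken from it is biased if the interaction changes over visits

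*SAP*

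**What the plan says.** The primary MMRM (SAP 8.1.1) has "treatment, visit, visit-by-treatment interaction, and weight category as fixed effects", with baseline score as a covariate. The sample code in SAP Appendix 1.1 agrees: "model chg = trtpn avisitn wtcat trtpn*avisitn base/ ddfm=kr2". On top of this, SAP 8.2.1 plans the following: "A sensitivity analysis will be done by adding an interaction term of treatment and weight category to the primary analysis model". Protocol 9.6.1 says the same.

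Neither document adds a weight-by-visit or treatment-by-weight-by-visit term, and the visible appendices contain no code for this sensitivity model. SAP Table 2 (8.2.7) nevertheless lists it as "Change from baseline in YMRS total score at Week 4 with interaction term of treatment and weight". The documents do not say which contrast will be reported from it.

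Weight category is the stratification factor and also sets the dose regimen. Under Protocol 5.3.2, the first-week titration cards "will have a maximum of 80 mg/day for subjects" of 45 kg or more, whose target range is 120-160 mg/day. On the standard second card that group reaches 120 mg/day on Day 10. Subjects below 45 kg are at 60 mg/day, inside their 60-80 mg/day target range, from Day 5. Protocol 1.4 describes titration over one week and two weeks respectively.

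**The concern.** A single treatment-by-weight coefficient, with no visit attached, is one number for Weeks 1, 2, 3 and 4 together. The Week 4 effects by weight group that the model yields differ by exactly that number, and the Type III test of the term tests that number. If the groups differ early and converge, the early difference is carried into Week 4. If they diverge late, the early visits dilute the difference.

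The titration schedule gives a reason to doubt constancy. At the Week 1 visit (Day 8) the lighter group is already in its target range and the heavier group, on the standard card, is not. In the visible text this is the only planned analysis that lets the treatment effect differ between the two weight-based regimens, so it is where a reader will look for consistency between them.

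The covariance choice does not cure this. SAP 8.1.1 states: "An unstructured covariance matrix will be used in the REPEATED statement", with empirical standard errors. Both concern the variance, whereas the constraint lies in the mean model.

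**Working it through.** **Inputs from the documents.** Week 4 difference -4.55, SD 8.0, 85% power, two-sided 5%, 111 required (SAP 2.2); 20% dropout and 138 subjects before the rater adjustment (SAP 2.2.1); four post-baseline visits; each weight category at least 20% of enrolment (Protocol section 4).

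**The plan's own figure.** Total N = 4 x (1.960 + 1.036)^2 x 8.0^2 / 4.55^2 = 111. This reproduces the stated 111, used below as the number evaluable at Week 4.

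**What the single term estimates.** Let g be the true interaction at each visit (effect below 45 kg minus effect at 45 kg or above) and S the 4x4 visit covariance. With treatment-by-visit in the model, and weight and treatment-by-weight constant over visits, the complete-data generalised least squares estimate is

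c = w'g, where w = S^-1 1 / (1' S^-1 1).

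**Assumptions, not in the documents.** SDs at Weeks 1-4: flat 8; 6.5, 7.3, 7.8, 8.0; or 5, 6, 7, 8. Correlations: compound symmetry (CS) 0.6; AR(1) 0.7; or 0.67, 0.635, 0.60 at lags 1, 2, 3. Two illustrative patterns:

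- (a) Effects at 45 kg or above -1.5, -3.5, -4.5, -4.55; below 45 kg -3.0, -4.5, -4.55, -4.55. So g = (-1.5, -1.0, -0.05, 0), and the true Week 4 interaction is 0.
- (b) Effects at 45 kg or above -2, -3, -4, -6; below 45 kg -3, -4, -4, -2. So g = (-1, -1, 0, +4), and the true Week 4 interaction is +4.

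Example, flat SD with CS: every weight is 0.25. For (a), c = 0.25 x (-2.55) = -0.64. For (b), c = 0.25 x 2 = +0.50.

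| SDs | Correlation | Weights, Weeks 1-4 | (a), truth 0 | (b), truth +4 |
|---|---|---|---|---|
| flat 8 | CS 0.6 | 0.25, 0.25, 0.25, 0.25 | -0.64 | +0.50 |
| flat 8 | AR(1) 0.7 | 0.38, 0.12, 0.12, 0.38 | -0.70 | +1.04 |
| flat 8 | 0.60-0.67 | 0.28, 0.22, 0.22, 0.28 | -0.65 | +0.61 |
| 6.5 to 8 | CS 0.6 | 0.52, 0.25, 0.13, 0.10 | -1.04 | -0.39 |
| 6.5 to 8 | AR(1) 0.7 | 0.59, 0.06, 0.06, 0.29 | -0.94 | +0.51 |
| 6.5 to 8 | 0.60-0.67 | 0.56, 0.21, 0.10, 0.12 | -1.06 | -0.27 |
| 5 to 8 | CS 0.6 | 0.73, 0.29, 0.06, -0.08 | -1.39 | -1.33 |
| 5 to 8 | AR(1) 0.7 | 0.74, 0.06, 0.06, 0.14 | -1.18 | -0.25 |
| 5 to 8 | 0.60-0.67 | 0.77, 0.25, 0.03, -0.06 | -1.41 | -1.26 |

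**Week 4 effects by group.** Let p be the share below 45 kg and D the share-weighted Week 4 difference. The model gives D + (1 - p)c below 45 kg and D - pc at 45 kg or above. The share-weighted average is p[D + (1 - p)c] + (1 - p)[D - pc] = D, so the overall difference is preserved. At p = 0.20:

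- (a) D = -4.55. The model gives -5.06 to -5.68 below 45 kg and -4.42 to -4.27 above; the truth is -4.55 in both.
- (b) D = 0.8 x (-6) + 0.2 x (-2) = -5.2. The model gives -4.37 to -6.27 below 45 kg (truth -2) and -5.41 to -4.93 above (truth -6).

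**Precision after the change.** The SE of the Week 4 interaction is sqrt[64 x (4/111) x (1/p + 1/(1 - p))], which is 3.80 at p = 0.20 and 3.10 at p = 0.40. Power for 4.55 points is Phi(4.55/3.80 - 1.96) = 22% and Phi(4.55/3.10 - 1.96) = 31%. Replacing 64 by w'Sw gives the SE of the common term; for flat SD with CS at p = 0.20, w'Sw = 64 x 2.8/4 = 44.8 and the SE is 3.18.

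**Dropout.** A simulation (138 subjects, 20% random monotone dropout, 25% below 45 kg, AR(1) 0.7, baseline covariate omitted) used two stronger patterns. With g = (0, 0, 2.28, 4.55) the stated model averaged 1.77 (flat SD) and 0.69 (SD 5 to 8). With g = (4.55, 3.03, 1.52, 0) it averaged 2.56 and 3.86. With the two extra terms the Week 4 interaction was recovered: 4.7 to 4.8 for a truth of 4.55, and 0.1 to -0.3 for a truth of 0 (Monte Carlo SE 0.17).

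**The case against.** The analysis is labelled a sensitivity analysis of the primary endpoint, and nothing promises weight-group effects. If its purpose is to see whether the overall Week 4 result survives the added term, the constraint does no harm at observed weight shares. This stands, and it limits the point to any group-specific effect or interaction test drawn from the model.

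A reader might infer that the model cannot estimate a Week 4 effect in either weight group. It can: treatment plus treatment-by-Week-4 plus, for one group, treatment-by-weight. That estimate is unbiased, and more precise than the visit-specific one, if the interaction is constant. The documents neither assume nor exclude constancy.

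A reader might also infer that the term is mainly an early-visit, titration-driven quantity. That depends on SDs that rise over visits, which the documents do not give. The Week 4 weight runs from about -0.08 to 0.38 over the cases above. On the standard cards both groups are in range before Day 15, so titration supports a difference mainly at Week 1. Pattern (b) is an illustration of cancellation and has no basis in the documents.

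The noise is large. The false interaction in (a) is less than one standard error in every case, so it would rarely be declared significant, and a true 4-point difference would usually be missed even by the corrected model. This bears on how the result is presented and does not justify the constraint.

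Finally, the fitted model might contain more than the prose lists. The pattern-mixture prose in SAP 8.2.1 names only two-way terms, but its code in Appendix 1.4 has "dropout dropout*avisitn dropout*trtpn avisitn*trtpn*dropout / solution covb". No such code is visible for the weight model, so the literal reading stands. The example also shows that a visit-specific group term already has a precedent in this SAP.

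**Conclusion.** The point holds in a limited form. As written, the model fixes the treatment-by-weight interaction across Weeks 1-4 while Table 2 calls the analysis a Week 4 one. Any Week 4 weight-group effect or interaction test taken from it is biased if the interaction changes over visits. Under the assumed covariances, a true zero is reported as about -0.6 to -1.4 points, and an illustrative true +4 as about -1.3 to +1.0, against a design effect of 4.55. These sizes rest on the assumed visit SDs, correlations and effect patterns; only the Week 4 SD comes from the documents.

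It would be wrong to infer that the primary result is at risk. The primary model does not contain the term, and the overall Week 4 difference at observed weight shares is unchanged. This is a cheap improvement to a supportive analysis.

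**What to change.** In SAP 8.2.1, specify this sensitivity model with weight-by-visit and treatment-by-weight-by-visit as well as treatment-by-weight, and add its code to the appendix. Align Protocol 9.6.1 and SAP Table 2.

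State the contrasts: the Week 4 ziprasidone-placebo difference with 95% CI in each weight group, and the Week 4 interaction estimate with CI. Present them descriptively and do not treat a non-significant interaction as evidence of equal effects.

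If an overall Week 4 difference is also reported from this model, state how the weight groups are averaged. Default least squares means weight them equally, which shifts the result by (0.5 - p) times the interaction: 0.3 x 4.55 = 1.4 points at p = 0.20 and an interaction of 4.55.

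The cost is SAP wording, a line or two of code and six more fixed-effect parameters (three for each added term). The primary analysis, data collection and sample size do not change. The downside is a wider CI, chiefly below 45 kg: at the 20% floor, 156 subjects give about 31 in that group, or roughly 12 per arm at Week 4 after 20% dropout.

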8.2.2. Sensitivity Analysis of the primary endpoint

The YMRS and/or KSADS data of 18 subjects were impacted by the rating training issue. A sensitivity analysis of the treatment effect on the primary endpoint, excluding these 18 subjects from the analysis, will use the MMRM analysis specified in the [Section 8.1.1](#). This analysis will be conducted on the ITT population only.

8.2.3. Secondary Analyses

The secondary efficacy endpoints include:

- *Change from baseline to week 4 in the CGI-S score (key secondary endpoint);*

- *Change from baseline to weeks 1, 2 and 3 in YMRS and CGI-S;*
- *Raw CGI-I score at weeks 1, 2, 3 and 4 (as opposed to change from baseline).*

These endpoints will be analyzed using the MMRM model described in [Section 8.1.1](#). The point estimates and 95% CIs for the difference in means between the two treatments will be constructed using the least squares means and appropriate standard errors.

Descriptive statistics for raw CGI-I scores and for change from baseline CGI-S scores will be provided by treatment group and visit classification.

CCI

8.2.5. Safety Analyses

The safety assessments include:

- *Adverse Event Reporting;*
- *Concomitant treatment*
- *Clinical Laboratory Testing;*
- *Physical Examinations;*
- *Blood Pressure and Pulse;*
- *Height and Weight, BMI, BMI z-score, and waist circumference;*
- *Electrocardiogram.*

A 3-tier analysis approach described below will be used to analyze adverse events. No formal statistical analysis will be conducted on any of the other safety data listed above.

Data for height, weight, BMI, and waist circumference will be summarized by timepoint using descriptive statistics. Additionally, height, weight, and BMI will be standardized using CDC growth charts and the resulting z-scores presented in listings and frequency tables in 1-unit intervals. In addition, frequency tables of above/below a 1-point increase in the z-scores for BMI will be presented.

All randomized subjects who receive at least one dose of study drug will be included in the safety analysis. All adverse events that are observed from the time of first dosing with study medication (at randomization) until the end of study participation will be included in the safety analysis. Adverse events that occurred during treatment with the antipsychotic medication will be reported separately if the event occurred prior to randomization.

All adverse events will be coded according to the Medical Dictionary for Regulatory Activities (MedDRA) and will be summarized by treatment group. The incidence of treatment-emergent adverse events will be tabulated by treatment group and by system organ class. In addition, the incidence of serious adverse events and adverse events that cause withdrawal will be tabulated. All adverse events will be listed.

The following 3-tier approach will be used to summarize AEs. Under this approach, AEs are classified into 1 of 3 tiers. Different analyses will be performed for different tiers and will be documented in the statistical analysis plan as follows:

Tier-1 events: These are pre-specified events of clinical importance and are maintained in a list in the product's Safety Review Plan. This list may be updated, as more is understood about the drug.

Tier-2 events: These are events that are not tier-1 but are "common". A MedDRA Preferred Term (PT) is defined as a tier-2 event if there are at least 4 in any treatment group.

Tier-3 events: These are events that are neither tier-1 nor tier-2 events.

The analysis of adverse events under the 3-tier approach is considered exploratory. There will be no adjustment for multiple comparisons or stratification factors in the analyses. For tier-1 and tier-2 events, the proportion of AEs observed in each treatment groups will be presented along with the point estimates and associated 95% confidence intervals of the risk difference for the ziprasidone group compared with placebo.

For tier-1 events p-values will be included in the presentations. AEs will be arranged in the output sorted in descending point estimate of the risk difference within system organ class. Footnotes in the outputs will include the methods used to derive any p-values and confidence intervals as per Pfizer standards. The tier-1 AEs will be analyzed using the approach of Chan and Zhang (1999)¹ who inverted two one-sided tests at half the significance level each for calculating P-values and confidence intervals. The list of tier-1 AEs is maintained in the Ziprasidone Safety Review Plan.

For tier-2 AEs, both proportion and 95% CIs will be generated using an asymptotic approach (Proc Binomial). A MedDRA PT is defined as a tier-2 event if there are at least 4 in any treatment group. A cross-industry expert team on safety planning, evaluation and reporting

(Crowe et al, 2009)³ suggests using the “Rule of 4” to define tier-2 events. The “Rule of 4” says that if a trial has 400 or fewer patients per group and there are 4 or more subjects with a given MedDRA PT in any treatment group, then that PT will be categorized as a tier-2 event.

For tier-3 events, simple proportions will be presented.

All clinical laboratory data will be subjected to clinical review, summarized by frequency of events and mean changes from baseline.

All vital sign measurements will be displayed in listings by subject for each sample collection date and time. The measurement taken immediately prior to randomization will be used as the baseline for calculating changes in vital signs.

Centrally over-read ECG variables will be summarized by mean change from baseline to each measurement time for heart rate, PR interval, QRS width, QT interval and QTcF (Fridericia correction) values. Baseline will be defined as the mean of the pre-dose triplicates at the Baseline Visit. Additionally, the incidence of categorical increases in QTc intervals will be provided. Categories for QTcF are ≥ 450 msec, ≥ 480 msec, and ≥ 500 msec. Categories for QTcF as change from baseline are ≥ 30 msec increase and ≥ 60 msec increase. QTcF is considered the primary QTc value for measurements of change and for clinical decision making as this correction is more accurate with changes in heart rate. To enable historical comparisons, categorical changes in QTcB (Bazett’s correction) also will be tabulated but clinical decisions and interpretation of data will be based on QTcF values.

The frequency of prior and concomitant medications will be summarized by treatment based on the WHO-drug coding dictionary.

